## STUDY SYNOPSIS

[figure not shown]
Title of Study:	Pain Management and Patient Education for Physical Activity in Intermittent Claudication (PrEPAID): Feasibility Randomised Controlled Trial
Study Centre:	Clinical Research Facility at Queen Elizabeth University Hospital/ Glasgow Caledonian University/ Robertson Centre for Biostatistics
Duration of Study:	26 months
Research aims:	
 
1. To determine the feasibility of conducting a definitive trial that would assess the effects of a TENS intervention with/or without patient-centred education on physical activity in people with intermittent claudication.
 
2. To collect preliminary data on the acceptability of TENS and patient education, both as separate and combined interventions in people with Intermittent Claudication (IC).
 

Research objectives:	
 
1. To estimate rates of recruitment, retention, intervention uptake and adherence, and outcome completion for a definitive RCT which would investigate the effects of TENS and/or patient-centred education in people with IC.
 
2. To determine the potential effect of the interventions on patient outcomes including walking, physical activity and PROMs
 
3. To explore participants' experiences and perceptions of the interventions and trial procedures via focus groups
 

Primary Endpoints:	
 
1. Proportion of eligible patients, after full screening, who agreed to be randomized; and proportion of randomised participants who successfully completed each of the trial arm (intervention and outcome measure assessment).
 
2. The Absolute Claudication Distance, assessed by a treadmill exercise using the Gardner treadmill protocol shall be assessed as the primary outcome for this feasibility trial.
 

Rationale:	This is a feasibility trial that primarily aim to assess the feasibility of conducting a definitive trial that would assess the effects of a TENS intervention with and without patient-centred education on physical activity in people with intermittent claudication. Therefore, successful delivery and uptake of interventions by patients and evidence of improvement in patient outcomes are the most important and compelling consideration to make decision regarding feasibility of a definitive trial.

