Trial design:

We will conduct a 2 x 2 parallel group (TENS versus placebo TENS x SEDRIC versus no additional education) feasibility RCT to compare use of TENS against placebo TENS with and without a patient-centred education programme. Permuted block randomisation will be implemented to allocate patients to trial arms. The intervention will last for 6 weeks, and patients recruited within the first eight months will be further followed up for 3 months. Outcomes assessments will be implemented at baseline, after six weeks treatment and at 3 months follow up. We will collect information regarding the recruitment rate, intervention uptake, outcome measure completion rate, attrition rate, blinding fidelity, efficacy related to the primary, secondary and other PROMs, and patients experience of intervention including acceptability and ease of intervention.

Randomisation:

A central randomisation facility (interactive voice response system, IVRS) will allocate the randomised therapy per patient. The IVRS, based at the Data Centre, will be available by telephone. Stratified permuted block randomization procedures will be utilised to allocate patients to groups (Patients allocation will be stratified by gender and age, ABPI values). Permuted block design (PBD) will be used to allocated patients to the PE+TENS, PE+Placebo TENS, TENS, Placebo TENS using 4-way randomisation throughout the whole time until the recruitment of a minimum of 20 subjects in the each of the larger comparison groups are achieved.

Sample size:

Details regarding sample size calculation can be found in section 8.7 of the full study protocol (version 2.0). Summarily, 16 participants per group will allow detection of an effect size of 1.0sd of ACD in active TENS group compared to placebo control. Allowing for 20% attrition, we will recruit 20 participants in each group, and therefore aim to recruit 80 patients.

Framework

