Measure participant's retention throughout the trial and reasons for withdrawal
Monitor, record, manage and follow-up defined adverse events in all groups
Measure uptake of intervention (log of TENS use and attendance at education) and acceptability of these interventions via a questionnaire
Measure blinding fidelity via TENS feedback questionnaire
Outcome completion rate – number of day activPAL is worn at each outcome time point.

Efficacy outcomes

Measurement will be obtained at baseline, following six weeks intervention and at 3 months follow up

Primary efficacy outcomes

Treadmill assessed Absolute Claudication Distance (ACD) (cm).

Secondary efficacy outcomes will include:

Physical activity capacity secondary outcomes

Treadmill assessed Initial Claudication Distance (ICD), assessed by a treadmill exercise using the Gardner treadmill protocol.¹⁹ Measurement will be obtained at baseline, following six weeks intervention and at 3 months follow.

Daily physical activity. We shall specify 3 days activPAL data at each measure as minimum for including patient activPAL data in the efficacy analysis. However, activPAL were time (number of day worn) will be also be reported as part of the feasibility analysis. For secondary efficacy analysis, activPAL data outcomes: total number of **i**) steps; **ii**) upright events; **iii**) walking events; **iv**) Event-based claudication index (ratio of walking events to upright events) participants undertake in a day.²⁰

PROM secondary outcomes

Disease specific quality of life will be as assessed using the Intermittent Claudication Questionnaire (ICQ).

Generic quality of life via the SF-36;

Pain quality will be recorded using the McGill Pain Questionnaire (MPQ) 5 minutes after every treadmill test.

Average Pain intensity in the past 7 days will be recorded using a Visual Analogue Scale

Illness beliefs and psychosocial determinants of health and behaviour will be recorded using the Illness Perception Questionnaire (IPQ), Geriatric Depression Scale (Short Form) (GDS-SF) and the Pain Self-Efficacy Questionnaire (PSEQ).

Qualitative Experience outcome

Analysis Methods

Feasibility and qualitative data analysis

Descriptive statistics will be used to characterize the groups at baseline and to present the feasibility outcomes.

Outcomes related to experience and perception via focus groups will be analysed by framework analysis.

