To determine the feasibility of conducting a definitive trial, descriptive statistics will be used to report the number and proportion of participants who meet the inclusion criteria, who consented to participating, and who dropped out during the trial. Also descriptive analysis will report compliance with intervention by recording participants' attendance to education session, follow up calls, attendance to TENS training session, (rate of use of TENS) rate of outcome measure completion, and total accelerometer wear time. Specifically, the TENS log (questionnaire) as well as inbuilt record of TENS device usage will both be used to analyse patients utilisation of TENS. Acceptability of TENS will be obtained by TENS feedback questionnaire

Further exploration will be carried out to determine factors that impact on propensity to participate looking at the difference in characteristics between participants and non-participants. If less than 10% of the individuals with PAD/IC in the clinic are eligible to participate, or if less than 10% of eligible patients agreed to participate, then the eligibility criteria and recruitment strategy will be adjusted prior to conducting a definitive trial. Adjustment of the recruitment strategy in a definitive trial will be made comparing the difference in the baseline characteristics between participants and non-participants. Similarly, association between participants' baseline characteristics and trial outcome will also inform decision on adjustment of recruitment strategy and stratification factors in the definitive trial. Data collection for the definitive trial will be adjusted based on the information related to type, quantity of missing data, and the mechanisms by which these data are missing.

The transcripts from the focus group discussions will be analysed using framework analysis. The data gathered from the exit interview will form part of acceptability analysis and be used to adapt the intervention to enhance its acceptability in a definitive trial.

Primary efficacy analysis

Differences in the change in ACD will be analysed and effect scores calculated using Chi-squared tests, Mann-Whitney U or Wilcoxon signed-rank tests as applicable for between and within-group comparisons and log-rank method for pooled samples or sub-strata. Baseline participants' variability will be controlled for using the analysis of co-variance.

Secondary efficacy analysis

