Recruitment target/Number recruited.					
Recruitment rate (n/centre/month)					
Outcome completion rate					
Reasons for withdrawal from intervention					
Retention rate (proportion of participants with valid primary outcome data at 3-months follow-up)					
Retention rate (proportion of participants with valid ActivPAL outcome data at 3-months follow-up)					
Reason for withdrawal from follow up					
Timing of withdrawal					
Intervention uptake and Adherence rate					
Attendance to PE					
Summary from phone calls					
TENS log summary					
Objective record of TENS use					
Acceptability of intervention					
Acceptability questionnaire					
Adverse events rate					
List them					
TENS blinding					

PrEPAID Statistical Analysis Plan (Version 1.0)
 Approval date:

Table 3: Changes in groups' outcomes at 6-wweks compared to placebo (usual care alone)

	TENS	PE+TENS	PE
ACD	$x \pm sd$ vs $x \pm sd$; $p=xxx(95\%cl)$		
ICD			
Daily steps			
Upright events			
Walking events			
EBCD			
ICQ			
SF-36			
7-day Average pain intensity			
Pain quality			
IPQ			
GDS-SF			
PSEQ			

*Also compare between PE+TENS and each of TENSs and PE alone (May not present in a table)

PrEPAID Statistical Analysis Plan (Version 1.0)
 Approval date:

Table 4: Changes in groups' outcomes at 3 months compared to placebo (usual care alone)

	TENS	PE+TENS	PE
ACD	$x \pm sd$ vs $x \pm sd$; $p=xxx(95\%cl)$		
ICD			
Daily steps			
Upright events			
Walking events			
EBCD			
ICQ			
SF-36			
7-day Average pain intensity			
Pain quality			
IPQ			
GDS-SF			
PSEQ			

*Also compare between PE+TENS and each of TENSs and PE alone ((May not present in a table)

Table 5: Within group comparisons between baseline and after 6 weeks intervention and 3 months follow up

	TENS	PE+TENS	PE	Usual care alone
ACD Post 6 wks Post 3 months follow up	$x \pm sd$ vs $x \pm sd$; $p = xxx$ (95%cl)			
ICD Post 6 wks Post 3 months follow up				
Daily steps Post 6 wks Post 3 months follow up				
Upright events Post 6 wks Post 3 months follow up				
Walking events Post 6 wks Post 3 months follow up				
EBCD Post 6 wks Post 3 months follow up				
ICQ Post 6 wks Post 3 months follow up				
SF-36 Post 6 wks Post 3 months follow up				
7-day mean pain intensity Post 6 wks Post 3 months follow up				
Pain quality				

PrEPAID Statistical Analysis Plan (Version 1.0)
Approval date:

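### The SAP defines outcome completion rate as days of activPAL wear, so the Table 2 row would not report completion of ACD or any questionnaire, and no completion proportion is defined at 6 weeks

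*SAP*

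**What the plan says.** The first primary endpoint in the protocol synopsis includes the "proportion of randomised participants who successfully completed each of the trial arm (intervention and outcome measure assessment"). Estimating outcome completion is also part of the first research objective in both documents.

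The SAP deals with completion in several places:

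- **Section 6, feasibility and acceptability outcomes.** Outcome completion rate is defined here, and nowhere else in either document, as the "number of day activPAL is worn at each outcome time point".
- **Section 6, feasibility and qualitative data analysis.** The descriptive analysis will report "rate of outcome measure completion, and total accelerometer wear time". These are two items, and the first is not defined there.
- **Section 6, daily physical activity.** "We shall specify 3 days activPAL data at each measure as minimum" for entry into the efficacy analysis. Days worn are to be reported as a feasibility item as well.
- **Table 2.** It has an outcome completion rate row for the whole sample and each arm. Two further rows are true proportions: "Retention rate (proportion of participants with valid primary outcome data at 3-months follow-up"), and the same for activPAL data.
- **Section 4, adherence and protocol deviations.** Intervention adherence is defined. Missed physical activity assessments and questionnaires are logged as deviations and summarised per group.
- **Section 3, trial design.** Only "patients recruited within the first eight months will be further followed up for 3 months".

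**The concern.** A completion rate needs a count of participants assessed and a count of participants who should have been assessed. A number of days per participant has neither. It also concerns one monitor-based secondary outcome, while the primary outcome is the treadmill ACD. An analyst who fills in Table 2 from the stated definition would put wear days in the row that answers the first objective.

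The plan needs the missing quantity for its own purposes. The SAP says that data collection in the definitive trial will be adjusted according to the type and amount of missing data. That calls for completion by instrument and by visit. A definitive trial sized on ACD would also need to know what fraction of randomised participants yield a valid ACD.

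**Working it through.** No figure in the documents is in dispute, so the check is mainly a comparison of texts. Two short calculations follow.

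**1. What the definition covers.** The post-intervention visit in protocol section 4.1 collects one treadmill test (ACD and ICD), activPAL, and seven questionnaires or scales: SF-36, ICQ, VAS, GDS-SF, PSEQ, IPQ and MPQ. That is 1 + 1 + 7 = 9 measures. The definition touches one of the nine. Blood would make ten, but the protocol's amendment summary describes the sample as optional, so I leave it out of the count.

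**2. What the rest of the SAP covers.**

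| Quantity needed | Where the SAP provides it |
|---|---|
| ACD completion, 6 weeks | Not defined as a proportion |
| ACD completion, 3 months | Table 2 retention row; denominator not stated |
| activPAL completion, 6 weeks | Wear days only |
| activPAL completion, 3 months | Table 2 retention row; denominator not stated |
| Questionnaire completion, either visit | Only as deviations, by number and type per group |
| Completion of intervention | Adherence definition, Section 4 |
| Composite: intervention and assessment | Not defined |

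All participants are due at 6 weeks. Only those recruited in the first eight months are due at 3 months. So the two proportions that the SAP does define apply to a subgroup whose size is not stated.

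**3. Days worn cannot be turned into completion.** The prescribed wear is 7 days and the planned arm size is 20. Take two hypothetical arms:

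- Arm A: 16 participants wear the monitor for 7 days and 4 do not wear it. Total 16 × 7 = 112 days; mean 112/20 = 5.6 days.
- Arm B: 12 wear it for 6 days and 8 for 5 days. Total 72 + 40 = 112 days; mean 112/20 = 5.6 days.

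The means are equal. The proportion with at least 3 days is 16/20 = 80% in A and 20/20 = 100% in B. Neither mean says anything about how many walked on the treadmill or filled in a questionnaire. At visit 4 the monitor is fitted and later posted back, so its data can be lost when every other assessment was done, and the reverse.

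**4. Precision of a properly defined proportion.** Protocol section 8.7 allows for 20% attrition, and attrition in its two pilots was 7.1% and 10%. I therefore assume completion of 80% to 90%. The Wilson 95% interval is

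[p + z²/2n ± z√(p(1−p)/n + z²/4n²)] / (1 + z²/n), with z = 1.96.

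For 16/20: (0.800 + 0.096 ± 1.96 × √(0.0080 + 0.0024)) / 1.192 = (0.896 ± 0.200) / 1.192, which gives 58.4% to 91.9%.

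| Assumed completion | Per arm, n = 20 | Overall, n = 80 |
|---|---|---|
| 80% | 16/20: 58.4% to 91.9% | 64/80: 70.0% to 87.3% |
| 90% | 18/20: 69.9% to 97.2% | 72/80: 81.5% to 94.8% |

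The overall figures are usable for planning. The per-arm figures are descriptive only.

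**The case against.** The strongest reply is that this line is not the SAP's only provision. The analysis text commits to a rate of outcome completion beside wear time, and the Framework paragraph promises completion rates by arm and overall. Table 2 defines a proportion with valid ACD data at 3 months. Missed assessments are summarised as deviations, withdrawals are reported with timing and reasons, and adherence has its own definition. A sensible analyst would probably report completion properly.

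Much of this stands. A reader might infer that the SAP has no route at all to the primary feasibility endpoint. The documents do not support that, because the provisions just listed are partial routes. A reader might also infer that good wear with poor treadmill completion would make the trial look feasible, or the reverse infeasible. That is not supported either. The only numerical triggers (protocol section 8.2, repeated in the SAP) are fewer than 10% eligible and fewer than 10% of eligible patients agreeing. No prespecified decision turns on completion or wear days, and poor ACD completion at 3 months would show in the retention row.

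The reply does not remove the conflict between the definition and the analysis text. Nor does it give a 6-week ACD proportion, a questionnaire rate or the composite. A deviation count is not a completion proportion over those randomised.

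It is also fair that the SAP plans descriptive summaries for feasibility data. Leaving out an interval on every cell is a choice, not an error.

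**Conclusion.** The definition is wrong as written: it names one quantity and describes another, and it contradicts the analysis text in the same section. Taken alone, it cannot supply the outcome-assessment part of the first primary endpoint. Other parts of the SAP fill some of the gap at 3 months for early recruits. Three things remain undefined as proportions: ACD completion at 6 weeks, completion of each questionnaire at either visit, and the composite of completed intervention and assessment.

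The effect is on reporting. It does not bias a treatment comparison or change a prespecified feasibility decision. The conclusion rests on the text alone. The 80% and 90% completion values serve only to show precision and are assumptions. The point should be settled before the analysis.

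**What to change.** 1. Relabel the Section 6 line as activPAL wear time and report it in its own Table 2 row.
2. Define completion for each outcome and visit as the number with valid data divided by the number randomised; at 3 months, divide by the number due that visit. Apply this to treadmill ACD, to activPAL with at least 3 valid days, and to each questionnaire, by arm and overall. State the 3-month denominator in the existing retention rows too.
3. Define the composite of completed intervention and outcome assessment as meeting the SAP Section 4 adherence definition and having a valid 6-week ACD.
4. Give a 95% confidence interval at least for ACD completion and the composite. Optional blood samples can be reported as uptake.

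The cost is small: a SAP wording change and added Table 2 rows, at most one for each of the nine measures if visits are shown side by side, plus the composite and wear time. No new data collection is needed. Per-arm intervals will be wide (about 58% to 92% at an assumed 80% completion), so the overall figures should carry the planning.

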Statistical Analysis:	
Descriptive statistics for participants' characteristics, recruitment and intervention completion rates will be used to analyse results related to the feasibility and acceptability outcomes. In addition, the transcripts from the focus group discussions will be analysed using framework analysis.
 
Patient outcomes - 95% CI will be analysed using Chi-squared tests, Mann-Whitney U or Wilcoxon signed-rank tests as applicable; and log-rank method for pooled samples or sub-strata.

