### Visit 2- Second Assessment Visit (usually within 2 weeks after visit 1):

Participants will then attend for a second visit to undergo a second Treadmill test, and to return the activPAL and sleep diary. Only participants with ≤20% variation in ACD will continue in the trial. After this visit eligible participants will be randomized, and given a date for them to return for intervention (TENS/Placebo ± Education) as applicable. Recruitment and randomisation will be done in waves to allow groups to be formed for the education session.

Second Assessment Visit (30 mins)	Time (mins)	Responsible
Return of ActivPAL by participants	5	RN/UA
Treadmill protocol • McGill Pain Questionnaire (5 minutes after completion of the treadmill protocol)	20	

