Differences in the changes in activPAL outcomes, ICD, SF-36 and ICQ scores, MPQ score, IPQ, GDS-SF, PSEQ, ABI, and Biomarkers will also be analysed and effect scores calculated using Chi-squared tests, Mann-Whitney U or Wilcoxon signed-rank tests as applicable for between and within-group comparisons and log-rank method for pooled samples.

Safety analysis

The safety data (adverse events)- both numbers of subjects and events – will be summarised by randomised group and overall using descriptive statistics. No formal statistical tests comparing the randomised groups will be pre-specified.

Software for statistical analysis

The statistical software to be used is either SAS 9.2 for Windows, Cary, NC, USA or SPSS Version 22.

PrEPAID Statistical Analysis Plan (Version 1.0)
 Approval date:

Table 1: Participant characteristics at baseline

	PE+TENS	PE+ Placebo TENS	TENS	Placebo TENS
Age				
Sex (%male)				
Ankle-brachial index				
Diagnosis of PAD				
Date of diagnosis:				
\geq 3months <6months				
\geq 6months<12months				
\geq 12months				
Type of PAD				
Iliac				
Femoral				
Popliteal				
Other				
Diagnosis of IC				
Date of diagnosis:				
\geq 3months <6months				
\geq 6months<12months				
\geq 12months				
Limb affected				
Left				

PrEPAID Statistical Analysis Plan (Version 1.0)

Approval date:

Right				
Both				
Fontaine Classification				
I				
II				
III				
IV				
Past Medical History				
IHD: Y/N				
MI: Y/N				
LVH: Y/N				
Cardiac risk factors				
DM : Y/N				
Family History of IHD/CVA/ BP: Y/N				
Hypercholesterolemia: Y/N				
Hypertension: Y/N				
Alcohol excess:				
Current				
Previous				

PrEPAID Statistical Analysis Plan (Version 1.0)

Approval date:

Never				
Smoking:				
Current				
Previous				
Non-smoker				
Present drug history:				
Statin Y/N				
Antiplatelet Y/N				
Anticoagulant Y/N				
Outcome measures				
Treadmill maximal walking distance				
Treadmill pain free walking distance				
Daily steps				
Pain intensity(VAS)				
McGill pain score				
QoL SF-36 score				
ICQ score				
Geriatric depression questionnaire score				
Pain self-efficacy questionnaire score				
Brief illness perception questionnaire				

Table 2: Feasibility related outcome tables

Participants recruitment					
Total number of participants screened(n)					
Total number of eligible participants (n/%)					
Reasons for non-eligibility					
X (n/%)	Whole study sample	PE+TENS	PE+ Placebo TENS	TENS	Placebo TENS

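### ACD has two unranked analyses, the secondary outcomes are compared by unadjusted change, and no efficacy model names the stratification factors

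*SAP*

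**What the plan says.** **ACD.** SAP Section 6, Primary efficacy analysis (repeated from Protocol 8.3): "Differences in the change in ACD will be analysed and effect scores calculated using Chi-squared tests, Mann-Whitney U or Wilcoxon signed-rank tests". The sentence then says where each method is meant to be used: "as applicable for between and within-group comparisons and log-rank method for pooled samples or sub-strata". The next sentence says that participants' baseline "variability will be controlled for using the analysis of co-variance". The methods are not ranked and the ANCOVA covariates are not listed.

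**Secondary outcomes.** The next SAP paragraph gives the same list of tests and log-rank, without the ANCOVA sentence. Its list of outcomes ends: "PSEQ, ABI, and Biomarkers will also be analysed and effect scores calculated using Chi-squared tests". Protocol 8.4 has a matching paragraph but does not include ABI.

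**Outputs.** SAP Section 4 (Analysis populations) promises effect sizes with 95% confidence intervals. The shells of Tables 3 and 4 ask for mean ± SD in each group, a p-value and a 95% CI, for each arm against placebo TENS. Their footnotes add PE+TENS against TENS and against PE. Table 5 uses the same format for change within each arm. The protocol synopsis says of patient outcomes: "95% CI will be analysed using Chi-squared tests, Mann-Whitney U or Wilcoxon signed-rank tests as applicable".

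**Randomisation and follow-up.** SAP Section 3: "Patients allocation will be stratified by gender and age, ABPI values". For the 3-month assessment: "patients recruited within the first eight months will be further followed up for 3 months". The size of that subgroup is not given.

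**The concern.** A feasibility trial that is to supply the effect size and SD for a definitive trial needs one stated estimator per outcome. Three things are missing.

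- **A lead ACD analysis.** A rank test on change and an ANCOVA can give different p-values and intervals. The SAP sets significance at p<0.05 and does not say which of the two is reported, so the choice could be made after the results are seen.
- **Use of data already collected.** Every secondary outcome in Tables 3 to 5 is measured at baseline, and sex, age and ABPI are known at randomisation. Comparing raw changes leaves most of that information unused.
- **Anything for chi-squared and log-rank to act on.** Neither document defines a responder cut-point, an event or a censoring rule for a change in a continuous outcome.

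A smaller matter is that Table 5 attaches p-values to change within an arm. The SAP introduction itself says that TENS has a strong placebo effect in pain, so such p-values cannot separate treatment from placebo or practice effects.

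**Working it through.** **The plan's own figure.** Protocol 8.7 gives 16 per group for 1.0 SD of ACD at 80% power, two-sided 5%. n = 2(1.960 + 0.842)² / 1.0² = 15.7, so 16. Then 16 / 0.80 = 20 per group, and 4 × 20 = 80. The figure reproduces.

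**Inputs for the precision check.** 16 completers per arm and four arms come from Protocol 8.7 and SAP Section 3. The correlation ρ between baseline and follow-up is in neither document, so 0.5, 0.7, 0.85 and 0.9 are assumed. Data are taken as normal with SD 1, so widths are in SD units.

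**Formulas.**
- t interval on change, two arms: width = 2 × t(30 df) × √(2(1−ρ)) × √(2/16).
- ANCOVA on own baseline and four-level group: 5 parameters, 64 − 5 = 59 df, width ≈ 2 × t(59 df) × √(1−ρ²) × √(2/16).

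At ρ = 0.5 the first is 2 × 2.042 × 1.000 × 0.3536 = 1.444. The second is 2 × 2.001 × 0.8660 × 0.3536 = 1.225. The reduction is 1 − 1.225/1.444 = 15%. Simulation also allows for chance imbalance in baseline and gives 14%.

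**Simulated reduction in 95% CI width, 6 weeks, 16 per arm.**

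| Assumed ρ | Width, t on change | Own baseline + group | Plus sex, age, ABPI, not prognostic | Plus sex, age, ABPI, explaining 10% of residual variance (assumed) |
|---|---|---|---|---|
| 0.5 | 1.43 | 14% | 12% | 16% |
| 0.7 | 1.11 | 9% | 6% | 11% |
| 0.85 | 0.78 | 5% | 2% | 7% |
| 0.9 | 0.64 | 3% | under 1% | 6% |

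With one term each for sex, age and ABPI the model has 8 parameters, leaving 64 − 8 = 56 df. About 1.4 percentage points of the full-model gain come from pooling the error over four arms, not from the covariates.

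**3 months.** Take 8 completers per arm as an assumption. The 8-parameter model (32 − 8 = 24 df, covariates not prognostic) is 9% and 4% narrower at ρ 0.5 and 0.7, then 1% and 2.5% wider at 0.85 and 0.9. Own baseline and group only is 15%, 10%, 5% and 4% narrower.

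**Two ACD analyses.** One contrast at 16 per arm with no true effect, proportion with p<0.05:

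| Assumed ρ | Mann-Whitney on change | ANCOVA | At least one |
|---|---|---|---|
| 0.5 | 4.7% | 5.3% | 7.6% |
| 0.7 | 4.2% | 5.1% | 6.9% |
| 0.85 | 4.2% | 4.7% | 6.3% |
| 0.9 | 4.8% | 4.7% | 6.5% |

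An independent repeat gave 6.6-8.1% for at least one, against 4.2-5.8% for either alone.

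**The case against.** The strongest reply is that this is a feasibility trial. Protocol 8.1 and SAP Section 4 say that clinical differences are not the primary purpose, and the statistician is blinded to allocation. Both points lower the stakes. Neither ranks the two ACD analyses, and the estimates are still meant to size a definitive trial.

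The gain is also modest and depends on assumed correlations. The comparator is a t interval, chosen because the table shells ask for means with a CI; the SAP itself lists Mann-Whitney. If sex, age and ABPI are not prognostic, adding them costs 2 to 3 percentage points against own baseline and group alone. All of this stands.

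Four stronger readings might be inferred, and the documents do not support them:
- **That the change comparisons are biased or invalid.** They are valid between randomised arms, and a change score already subtracts baseline. What is absent is covariate adjustment.
- **That ACD is not adjusted at all.** ANCOVA is named for it. Its role and covariates are what is unstated. Reading the list as Mann-Whitney between arms and signed-rank within arms is fair, but does not help chi-squared or log-rank.
- **That the treadmill baseline is undefined.** Protocol 4.1 counts the Visit 1 treadmill test among the baseline measurements. At Visit 2, "Participants will then attend for a second visit to undergo a second Treadmill test", and that test serves the 20% variation check for eligibility.
- **That ABI is a planned outcome.** The protocol's amendment record says ABPI is not to be analysed and is needed only to control for baseline differences. Protocol 8.4 and SAP Tables 3 to 5 do not list it, so the entry in the SAP's secondary paragraph looks like a leftover. The same remark shows an intent to adjust for baseline ABPI, which the analysis section does not carry through.

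**Conclusion.** The point holds as one of specification and precision; it is not a bias correction. ACD has two named analyses with no lead, the secondary outcomes have only unadjusted tests of change, no efficacy model names the stratification factors, and two listed tests cannot be applied to changes as written.

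At 6 weeks, adjusting for own baseline and group would narrow intervals by about 14%, 9%, 5% and 3% at ρ 0.5, 0.7, 0.85 and 0.9. Adding sex, age and ABPI changes this to between under 1% and 12% if they carry no information, or 6% to 16% if they explain 10% of the residual variance. Fixing the lead analysis also removes the excess over the nominal 5%, about 6-8% when either ACD test may be reported. These sizes assume normal data, equal arms and the stated ρ; the documents give no ρ and no size for the 3-month subgroup. The change is worth making because it is almost free. The trial's validity does not depend on it.

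**What to change.** Amend SAP Section 6 before unblinding:

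1. **6 weeks.** Make ANCOVA the lead analysis for ACD and every continuous secondary outcome. Include the outcome's own baseline, the four-level randomised group, sex, age and ABPI. Use Visit 1 as the baseline, unless the mean of Visits 1 and 2 is named in advance for the treadmill outcomes.
2. **3 months.** Use own baseline and group only, because only those recruited in the first eight months are followed.
3. **Contrasts.** Report adjusted differences with 95% CI for each arm against placebo TENS, and for PE+TENS against TENS and against PE+placebo TENS, as the Framework paragraph and the footnotes to Tables 3 and 4 already plan. Take any pooled comparison from the same model.
4. **Other tests.** Keep Mann-Whitney on change as a sensitivity analysis. Remove chi-squared and log-rank for changes.
5. **Table 5.** Show within-arm changes with CIs and no p-values.
6. **ABI.** Remove it from the change outcomes in the secondary paragraph, and use ABPI as a baseline covariate.

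The cost is wording. All covariates are already collected, and the target of 80 need not rise: for 1.0 SD at 80% power, baseline-adjusted ANCOVA needs 12 per arm at ρ 0.5 and 9 at ρ 0.7. The downside is the small loss of precision at 6 weeks if the stratification factors turn out not to be prognostic.
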